4.2. Study Design Rationale

This is a contralateral 2x2 crossover trial with primary objective to evaluate initial comfort at 1-min, 5 min, 45 min and 2-hours post-fit of 3 reusable contact lenses soaked in 3 lens care solutions. This design was considered because patient-specific factors that might affect initial comfort such as tear film quality and burning/stinging tolerance level are well controlled. A washout period of 5-7 days was implemented between each exposure, including exposure to habitual solution, to reduce any potential carry-over effect that may bias the results. However, this design is not optimal for any potential bias associated with dominant eye effect, inter-eye interactions. Another limitation is associated with compliance problems such as subjects mixing up which eye each lens is in.

4.3. Enrollment Target and Study Duration

A total of up to 120 subjects (i.e. 40 per study lens) will be enrolled (informed consent signed). The goal is for a sample size of approximately 90 subjects (i.e. 30 per study lens) after subjects who withdraw or are lost to follow-up.

The Investigator is responsible for ensuring that all subjects entering the study conform to subject selection criteria. The number of subjects targeted for randomization and completion are as follows:

The number of subjects targeted for randomization and completion are as follows:

Table 1: Target number of subjects by arm and site

	ACUVUE 2	OASYS	Vita	Total
Randomization	36	36	36	108
Completion	30	30	30	90
Number of sites				4
Number of subjects/site	25-35	25-35	25-35	90-120
Min-Max				

The study will last approximately four weeks for each subject and the entire study duration will be approximately 4 months and include a 2-month enrollment period.

Once the informed consent has been signed the subject will be considered enrolled.

5. TEST ARTICLE ALLOCATION AND MASKING

5.1. Test Article Allocation

Subjects, in blocks of three, will be first randomly assigned to one of the three study lens types to wear throughout the study (ACUVUE 2, ACUVUE OASYS, ACUVUE Vita). Within each study lens, a contralateral 2-treatment x 2-period crossover design will be used to randomly assign subjects to wear 2 pair of lenses soaked in control solutions (CLEAR CARE and Opti-Free) and test solution (RevitaLens). Subjects in block of two will be randomized to one of the following sequences:

Sequence	Period 1	Period 2
Sequence 1	OPTI-FREE - RevitaLens	CLEAR CARE – RevitaLens
Sequence 2	CLEAR CARE – RevitaLens	OPTI-FREE - RevitaLens

At each period, subjects will be exposed to a control solution (OPTI-FREE or CLEAR CARE) in one eye and to a test solution (RevitaLens) in the contralateral eye for 2 hours using pre-soaked contact lenses. The test and control solutions will be randomly assigned to left and right eyes. A washout period will be incorporated between lens wear periods where subjects will be wearing 1-Day ACUVUE Moist, a daily disposable lens, for 5 to 7 days.

The randomization will be stratified by site and each site will receive separate randomization scheme. The study site will follow the randomization scheme provided and will complete enrollment according to the randomization list and will not pre-select or assign subjects. The assignment of the subjects must be performed at the first baseline visit (Visit 1). The following must have occurred prior to randomization:

- Informed consent has been obtained
- Subject meets all the inclusion / exclusion criteria
- Subject history and baseline information has been collected

The randomization scheme will be generated using the PROC PLAN procedure from the SAS Software Version 9.4 or higher (SAS Institute, Cary, NC).

5.2. Masking

This is a double masked study where subjects and investigators are masked to the identity of the study lenses and lens care solutions. Every attempt will be made to keep the personnel involved in the data collection unaware of the identity of study lenses and solutions.

The identity of lens care solutions will be not masked due to the differences in shape and color of the bottles. To maintain the masking of lens care solutions two investigator designees (i.e. sub-investigator and clinical coordinator) who are not involved in data collection will be responsible for soaking the lenses in the solutions per the randomization scheme and putting them in lens cases and handing them over to subjects for insertion.

The identity of the study lenses will be masked by over labeling the blister packs with a label containing the study number, lot number, sphere power, expiration date and the

randomization codes. Only the personnel involved in the over labeling and the Statistician generating the randomization scheme will have access to the decode information translating the randomization codes into test and control groups. The medical monitor will also have access to the decode information in case breaking the mask is necessary for the urgent medical treatment of a subject.

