6. STUDY INTERVENTION

6.1. Identity of Test Articles

The following contact lens will be used in this study:

Table 2: Test Article

	Washout Lens	Randomization lens Arm 1	Randomization lens Arm 2	Randomization lens Arm 3
Name	1-DAY ACUVUE® MOIST	ACUVUE® 2	ACUVUE® OASYS®	ACUVUE® Vita®
Manufacturer	Johnson and Johnson Vision Care, Inc.			
Compass Protocol(s)	17CP1339	17CP1339	17CP1339	17CP1339
Lens Material	Etafilcon A	Etafilcon A	Senofilcon A	Senofilcon C
Nominal Base Curve @ 22°C	8.5	8.3	8.4	8.4
Nominal Diameter @ 22°C	14.2	14.0	14.0	14.0
Nominal Distance Powers (D)	-1.00 to -6.00D	-1.00 to -6.00D	-1.00 to -6.00D	-1.00 to -6.00D
Modality in Current Study	Daily	Daily	Daily	Daily
Replacement Frequency in Current Study	Daily	Daily	Daily	Daily
Packaging Form (vial, blister, etc.)	Blister	Blister	Blister	Blister

All Subjects will wear Moist and will be randomized into one of the other lens types. Each subject will wear approximately fifty 1-DAY ACUVUE® MOIST® and eight of the other lens type.

The following lens care systems will be used in this study:

Table 3: Lens Care Systems

	Test	Control 1	Control 2
Solution Name/Description	Revitalens®	OPTI-FREE PureMoist	Clear Care
Manufacturer	Johnson & Johnson, Inc	Alcon, Inc	Alcon, Inc

Lenses will be soaked in the appropriate solution by an unmasked staff member at the site and transferred to the investigator in an unmarked lens case for lens insertion by the subject.

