		
 • Subjects may use reading glasses over study contact lenses as needed • A patient instruction guide will be provided. • Subjects will be scheduled for Visit 2 in approximately 5-7 days. 
* Note: In the event a lens is lost or damaged, the subject will return to the clinical site for replacement. As much as reasonably possible, a damaged lens and packaging should be returned to the clinical site (wet, if possible) and then returned to the Sponsor. If lens damage is present, complete the Product Quality Complaint Form, if applicable. The lens will be stored in labeled vial with study provided solution, and clearly differentiated from the other worn lenses that will be shipped back to the Sponsor.

1.26	Randomization	Subjects will be randomized to a contact lens arm and a solution order. The same power lenses as fit in Visit 1 will be used in all remaining visits. (this will allow time for lenses to be soaked 16-28 hours)

Prior to Visit 2, randomized lenses will be prepared.

Sixteen to twenty-eight hours prior to Visit 2, the subject's lenses will be soaked in the test solutions in the sponsor provided lens cases. (See work aid for lens preparation instructions)

VISIT 2

The subjects must present to Visit 2 wearing their habitual spectacles (if applicable) having not worn any lenses or used any artificial tears that day.

Visit 2: Follow-up of Washout lenses		
Step	Procedure	Details
2.1.	Adverse Events and Concomitant Medications Review	Review any changes to the subject's medical history or concomitant medications from the previous study visit. Record any changes, and any adverse events.
2.2.	Compliance	Confirm compliance with the dispensed Washout lenses.

Visit 2: Follow-up of Washout lenses		
Step	Procedure	Details
2.3.	Subject Reported Ocular Symptoms	Subjects will respond to a verbal open-ended symptoms questionnaire. [REDACTED]
2.4.	Follow-Up modified CLDEQ-8 Questionnaires	The subject will respond to the Follow-Up modified CLDEQ-8 Questionnaires. Note: instruct the patient to think about how their wash-out contact lenses feel on an average day and answer the questions based on this level of comfort. Appendix A
2.5.	Visual Acuity	Record the distance Snellen visual acuity with their habitual spectacles (OD, OS, and OU) to the nearest letter. Subjects must read the smallest line until at least 50% of the letters are read incorrectly. [REDACTED]

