2.6.	Slit Lamp Biomicroscopy	FDA Slit Lamp Classification Scale will be used to grade the findings and determine eligibility. If there are any Grade 2 or higher corneal staining or conjunctival injection, or Grade 3 or higher other slit-lamp findings, the subject is ineligible to continue at this time, but may return up to one additional time to determine eligibility. If discontinued a final examination must be completed. All adverse events must be followed to resolution. Note 1: The following [REDACTED] will be used to assess specific ocular physiology in greater detail: 
• [REDACTED] Limbal and conjunctival redness• [REDACTED]: Expanded Corneal staining• [REDACTED] Conjunctival staining If the clearance of the fluorescein needs to be expedited, preservative-free rewetting drops or saline may be instilled. [REDACTED]
2.7.	Confirm Eligibility	Confirm subject is still eligible to continue [REDACTED]

Visit 2: Lens pair #1 Fitting		
Step	Procedure	Details
2.8.	Lens Selection	Following the randomization scheme, lenses will be selected. The same lens power as worn in V1 will be used. Lenses will have been soaked for 16-28 hours in [REDACTED]

Visit 2: Lens pair #1 Fitting		
Step	Procedure	Details
		the study solution as specified by randomization scheme. The investigator must inspect the lenses and lens case for damage prior to the subject inserting the lenses. (See work aid for lens preparation instructions)
2.9.	Lens Insertion	The subject inserts the study lenses. Check for lens damage under the slit lamp before proceeding with lens settling. If the lens is damaged, the visit will be stopped, an exit slit lamp and visual acuity will be completed and the subject will be discontinued from the study.
2.10.	1-minute Post-Fit VAS Questionnaire	The subject will respond to the Post-Fit VAS Questionnaire.
2.11.	5-minute Post-Fit VAS Questionnaire	The subject will respond to the Post-Fit VAS Questionnaire.
2.12.	Subject Reported Ocular Symptoms	Subjects will respond to a verbal open-ended symptoms questionnaire.
2.13.	Visual Acuity	Record the distance Snellen visual acuity with the contact lenses (OD, OS) to the nearest letter. Subjects must read the smallest line until at least 50% of the letters are read incorrectly.

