If you do not intend to wear your lenses immediately after disinfection/neutralization, you may store them in the unopened lens case for up to 7 days. Disinfect and neutralize once a week with fresh solution and before wearing your lenses.

ACTIONS:

When used as directed CLEAR CARE solution provides a unique cleaning action, which removes film and debris from the lens surface. CLEAR CARE solution also helps prevent serious eye infections by killing harmful microorganisms on contact lenses.

INDICATIONS (Uses):

For simultaneous cleaning, daily protein removal, disinfecting, and storing of soft (hydrophilic) or rigid gas permeable (fluoro silicone acrylate and silicone acrylate) contact lenses as recommended by your eye care practitioner.

CONTRAINDICATIONS (Reasons not to use):

There are no known contraindications for use of CLEAR CARE Cleaning & Disinfecting Solution; however, if you are allergic to any ingredient in this solution, do not use.

WARNINGS:

Never put CLEAR CARE Cleaning & Disinfecting Solution on your lenses and insert directly into the eye. Lenses must be soaked in the provided lens case for 6 hours (neutralization process) prior to lens insertion. OTHERWISE, BURNING AND STINGING WILL RESULT.

Only use the special CLEAR CARE lens case for disinfection and neutralization. Do not use a flat case.

While rubbing RGP lenses with CLEAR CARE solution, some users may experience a mild, temporary skin discoloration (bleaching) of the fingers or hands. Always wash and rinse your hands after rubbing your lenses with the solution.

NEVER PUT CLEAR CARE SOLUTION THAT HAS NOT BEEN NEUTRALIZED IN YOUR EYES. If unneutralized CLEAR CARE solution gets in your eyes, remove your contact lenses immediately, and flush (wash) your eyes with a large amount of water or sterile saline for a few minutes. If burning or irritation continues, seek immediate assistance from an eye care professional. The red snap cap indicates that CLEAR CARE Cleaning & Disinfecting Solution should never be put directly in your eye.

PROBLEMS WITH CONTACT LENSES AND LENS CARE PRODUCTS COULD RESULT IN SERIOUS INJURY TO THE EYE.

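### Sections 5.2 and 6.4 have unmasked staff hand the soaked lenses to the subject, Section 6.1 sends them through the investigator; the plan should keep one route and name the case used at hand-over

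*Combined protocol and SAP*

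**What the plan says.** **Masking standard.** Section 5.2 says that "subjects and investigators are masked to the identity of the study lenses and lens care solutions". Because the bottles differ visibly, whoever soaks the lenses knows the solution, so the section gives that job to "two investigator designees (i.e. sub-investigator and clinical coordinator) who are not involved in data collection".

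**Route A (Sections 5.2 and 6.4, same text).** The same designees are responsible for "putting them in lens cases and handing them over to subjects for insertion". The recipient is the subject. The case is not described.

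**Route B (Section 6.1, text after Table 3).** An unmasked staff member soaks the lenses, which are then "transferred to the investigator in an unmarked lens case for lens insertion by the subject". The recipient is the investigator, and the case is unmarked.

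**Visit steps (Section 7.2).** Step 2.8 says "The investigator must inspect the lenses and lens case for damage prior to the subject inserting the lenses". Steps 4.8 and 5.8 repeat this. Step 3.8 does not.

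**Soaking vessel.** Before each of Visits 2 to 5 the lenses are "soaked in the test solutions in the sponsor provided lens cases", with a pointer to a work aid that is not among the documents. The CLEAR CARE insert in Appendix C says "Only use the special CLEAR CARE lens case for disinfection and neutralization. Do not use a flat case". It also bars other disinfecting solutions from that case. The RevitaLens insert asks for its own included case.

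**The concern.** The subject is the assessor. Comfort is scored on a visual analogue scale from 1 minute after insertion, and the Section 14.5 model compares solutions using eye-level scores from subjects who wear test in one eye and control in the other. In that setting, excluding the designees from data collection does not separate the person who knows the allocation from the person who produces the primary data. Route A puts the two in contact at the moment of hand-over. Even an unintended cue about which eye holds which solution would act on the contrast that the trial is built to estimate.

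A site that reads Section 5.2 and a site that reads Section 6.1 would also run the hand-over differently. With four sites and randomization stratified by site, masking conditions could then vary by site for no planned reason.

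A second, smaller gap is that the plan never says what container the masked investigator and the subject see. The word unmarked covers labels, not shape.

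**Working it through.** The plan gives no figure on this point, so the check is a comparison of texts and a count.

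**1. The two routes side by side**

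| Place | Who hands over | To whom | Case |
|---|---|---|---|
| Sections 5.2 and 6.4 | Designees who soaked the lenses | Subject | Not described |
| Section 6.1 | Unmasked staff member | Investigator | Unmarked |
| Steps 2.8, 4.8, 5.8 | Not stated | Investigator inspects before insertion | Case is inspected |
| Step 3.8 | Not stated | No inspection written | Not mentioned |

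The first two rows name different recipients. The third row requires lenses and case to be in the investigator's hands before insertion, which agrees with Section 6.1. Step 3.8 agrees with either route.

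**2. Fittings touched by the route conflict**

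- Visits 2, 3, 4 and 5 each have one study-lens fitting: 4 per subject.
- At the completion target of 90 (Section 4.3, Table 1): 90 × 4 = 360 fittings.
- At the randomization target of 108: 108 × 4 = 432 fittings.

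**3. Fittings where the case at hand-over matters most**

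- Each sequence in Section 5.1 has exactly one CLEAR CARE period, and each period has two fittings: 2 of 4 per subject.
- Totals: 90 × 2 = 180 of 360, or 108 × 2 = 216 of 432.
- In lenses: 4 fittings × 2 eyes = 8 per subject, matching the eight stated in Section 6.1. CLEAR CARE accounts for 2 of the 8 (25%), and for 2 of the 4 control lenses (50%).

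**4. Why those fittings differ**

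At a CLEAR CARE fitting the other eye always receives a RevitaLens-soaked lens. Read with their inserts, the two products are not soaked in the same vessel. Unless both lenses are then presented in matching cases, the container could distinguish the eyes. Section 5.2 names soaking first and placing in cases second, and Section 6.1 mentions the unmarked case only after soaking. Both can be read as soak, then transfer. Neither says so outright, and the text before each visit has the soaking itself done in the sponsor's cases.

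These are counts of occasions on which the wording matters. They do not estimate how often masking would be lost, or any bias in comfort scores; the documents give no basis for either.

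**The case against.** **Route A may be shorthand, and contact is not disclosure.** Handing lenses to subjects could mean by way of the investigator. The designees collect no data, Section 6.1 makes the case unmarked, and receiving a case from an informed person does not tell the subject which eye has which solution. This stands as far as it goes: nothing shows that masking would be lost. It does not remove the conflict, because the recipients as written differ and Section 5.2 is where a site would look for the masking procedure.

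**The work aid may settle preparation.** It may well describe vessels and transfers. That is a good reason not to call the soaking procedure deficient. It would not cure the disagreement between Sections 5.2 and 6.4 and Section 6.1, which would remain in the protocol.

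**A stronger reading is tempting.** A reader might infer that all lenses are soaked in one shared case against the CLEAR CARE insert, so that un-neutralised lenses reach the eye and lower early comfort for that control, or that the case shape gives the CLEAR CARE eye away. The documents support neither. No section prescribes a shared or flat case. The wording about sponsor-supplied cases is compatible with CLEAR CARE's own case. Section 1.2 commits to on-label use. The planned 16 to 28 hour soak exceeds the insert's 6-hour minimum. Soaking in the product case and presenting in an unmarked one is a natural reading. These remain possibilities that the text leaves open, not errors that it shows.

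**It is a pilot.** Section 2.3 calls the hypotheses exploratory. That limits the consequences, but Section 14.2 says the data will be used to design a future evaluation, so a cheap protection of a subjective endpoint is still worth having.

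**Conclusion.** The point holds as an internal conflict with a cheap remedy. The plan states two hand-over routes that cannot both be followed as written. It affects 4 of 4 fittings for every subject, and the Section 5.2 and 6.4 version brings a person who knows the allocation into contact with the subject who rates the primary endpoint. The unnamed presentation case is a secondary gap, most relevant to 2 of 4 fittings per subject.

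The conclusion rests on reading the recipients literally and on taking the investigator in Section 6.1 and at steps 2.8, 4.8 and 5.8 to be the masked one, as Section 5.2 implies. It does not assume that any cue is given, that any lens is soaked wrongly, or that the work aid is silent. It is a worthwhile correction rather than a threat to the validity of the study.

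**What to change.** 1. **One route.** In Sections 5.2 and 6.4, replace direct hand-over to the subject with the Section 6.1 route: the designees pass the prepared lenses to the masked investigator, who inspects them and gives them to the subject to insert.
2. **One presentation case.** State in all three sections that both lenses of a pair reach the investigator in identical unmarked cases, whatever vessel they were soaked in. Allow only what is needed to tell right from left, since Section 4.2 already lists mixing up the eyes as a limitation.
3. **Step 3.8.** Add the inspection sentence that steps 2.8, 4.8 and 5.8 carry.
4. **Soaking wording.** Reconcile the text before Visits 2 to 5 with the Appendix C inserts and the work aid, so that a reader can tell which vessel is meant for each solution. This review takes no position on which soaking procedure is right.

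**Cost.** Wording in four places and, where it is not already done, one transfer by staff already assigned. The downside is slightly more lens handling and a small added risk of damage. That is not trivial here, because steps 2.9, 3.9, 4.9 and 5.9 discontinue a subject whose lens is found damaged after insertion. Inspection before insertion at all four visits partly offsets it.

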5.3. Procedures for Maintaining and Breaking the Masking

Under normal circumstances, the mask should not be broken until all subjects have completed the study and the database is finalized. Otherwise, the mask should be broken only if specific emergency treatment/course of action would be dictated by knowing the treatment status of the subject. In such cases, the Investigator may, in an emergency, contact the medical monitor. In the event the mask is broken, the Sponsor must be informed as soon as possible. The date, time, and reason for the unmasking must be documented in the subject record. The Investigator is also advised not to reveal the study treatment assignment to the clinical site or Sponsor personnel.

When dispensing test articles, the following steps should be followed to maintain randomization codes:

1. Investigator designee (documented on the Delegation Log) will consult the lens fitting schedule/randomization scheme to obtain the test article assignment for that subject prior to dispensing
2. Investigator designee will record the subject's number on the appropriate line of the randomization scheme
3. Investigator designee will pull the appropriate test articles from the study supply. All test articles that are opened, whether dispensed (placed/fit on eye or dispensed outside the clinical site) or not, must be recorded on the Test Article Accountability Log in the "Dispensed" section

6. STUDY INTERVENTION

6.1. Identity of Test Articles

The following contact lens will be used in this study:

Table 2: Test Article

	Washout Lens	Randomization lens Arm 1	Randomization lens Arm 2	Randomization lens Arm 3
Name	1-DAY ACUVUE® MOIST	ACUVUE® 2	ACUVUE® OASYS®	ACUVUE® Vita®
Manufacturer	Johnson and Johnson Vision Care, Inc.			
Compass Protocol(s)	17CP1339	17CP1339	17CP1339	17CP1339
Lens Material	Etafilcon A	Etafilcon A	Senofilcon A	Senofilcon C
Nominal Base Curve @ 22°C	8.5	8.3	8.4	8.4
Nominal Diameter @ 22°C	14.2	14.0	14.0	14.0
Nominal Distance Powers (D)	-1.00 to -6.00D	-1.00 to -6.00D	-1.00 to -6.00D	-1.00 to -6.00D
Modality in Current Study	Daily	Daily	Daily	Daily
Replacement Frequency in Current Study	Daily	Daily	Daily	Daily
Packaging Form (vial, blister, etc.)	Blister	Blister	Blister	Blister

All Subjects will wear Moist and will be randomized into one of the other lens types. Each subject will wear approximately fifty 1-DAY ACUVUE® MOIST® and eight of the other lens type.

The following lens care systems will be used in this study:

Table 3: Lens Care Systems

	Test	Control 1	Control 2
Solution Name/Description	Revitalens®	OPTI-FREE PureMoist	Clear Care
Manufacturer	Johnson & Johnson, Inc	Alcon, Inc	Alcon, Inc

Lenses will be soaked in the appropriate solution by an unmasked staff member at the site and transferred to the investigator in an unmarked lens case for lens insertion by the subject.

